**2. What are the statistical considerations for the protocol?**

- This is a prospective, randomized double blind study. Subjects will be randomized to antibiotic (80mg tobramycin/40mL saline) or placebo arm (40mL of 0.9% saline).
- The primary objective of this study is to evaluate the efficacy of local antibiotics in decreasing incidence of infection. The primary outcome will include evidence of infection in the first 6 weeks of surgery. Infection will be defined as major and minor, with major indicated by return to the operating room for irrigation and debridement. Minor infection is represented by documentation of cellulitis or superficial infection at surgical site and administration of oral antibiotics. .
- Superficial infection as indicated by documentation of cellulitis at surgical site and administration of oral antibiotics with the indication of wound problems. The primary purpose of this study is to document infection rates in the first 6 weeks after surgery. If an infection is found, it will be cared for per standard clinical care; however, it will not be followed for research purposes.
- There will be no contingencies for early stopping as the patients are receiving a single dose of antibiotics. There will be no interim analysis or stratification factors
- We expect approximately - 60 – 65 open fractures within a year to be treated at UVA based on historical records.

We will use a one-sided test for proportions to compare the control and experimental groups for the primary endpoint (presence of infection) and the secondary endpoint of evidence of non-union. A p-value less than 0.05 will be considered a significant result.

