**3. Provide a justification for the sample size used in this protocol.**

A sample size analysis was completed for different alpha and power levels. A one-sided test for proportions was chosen to compare the baseline (no treatment) group to the hypothesized proportion (treatment group); based on historical data, we assumed that the no treatment group would have a 10% infection rate, and the treatment group would have a 1% infection rate. Using an alpha of 0.05 and power of 70%, we would need to have 60 patients in each group.

With an expected accrual rate of 65 patients per year, we would expect to enroll 130 patients in two years. In order to maintain the sample size needed to ensure statistically valid results, we would want to enroll approximately 133 patients over the study period to end up with at least 120 patients in the analysis.

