**2. Describe the type of information you will receive from each site.**

Answer/Response: We will receive de-identified subject demographics, infection information, pertinent dates, surgical procedures performed, and information re: treatment

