### Biomedical Research

**1. What will be done in this protocol?**

Patients who present with open fractures to UVA Health System will be approached for participation in the study. After obtaining Informed consent, subjects will be randomized to Antibiotic Arm (experimental) or Placebo. Administration of the local antibiotic in this study is being done solely for answering a research question on the efficacy of the antibiotic tobramycin in decreasing the risk and rate of infection.

Subjects will be randomized to the experimental group, who will be injected locally at the wound cavity (i.e. fracture site, surrounding soft tissue which include muscle, and subcutaneous space) with 80mg/40mL of tobramycin after wound closure, and placebo group who will be injected locally with 40 mL 0.9% NS after wound closure. Systemic antibiotic will not be withheld and will be done along side the local injection of tobramycin. If patient returns to the OR for repeat debridement procedures, the injection will be repeated. If patient returns to the OR for repeat debridement procedures, the injection will be repeated. The second injection will only be given if the subject undergoes a repeat procedure, and will be given two days later than the first injection. By this time, serum tobramycin levels would have normalized, given the low doses and time interval. . Dose volume will not be adjusted because the safety of this antibiotic assumes that the patient weighs at least 16 kg, and any patient 18 years or older will weigh more than that. While systemic antibiotic treatment is standard of care, animal studies and early clinical case series data indicated that injection of aqueous aminoglycoside after wound closure locally could be a highly effective technique for wound infection prophylaxis[1]. In this study protocol, other aminoglycosides (eg. Gentamycin) will be allowed as part of standard systemic prophylaxis.

Follow up data will be collected at 2 weeks, 6 weeks. Clinical data will be collected from medical records

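### The primary endpoint does not say that infection must be the reason for a return to the OR for irrigation and debridement, and it leaves out cellulitis treated only with IV antibiotics

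*Combined protocol and SAP*

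**What the plan says.** Statistical Considerations item 2 sets the outcome and its window: "The primary outcome will include evidence of infection in the first 6 weeks of surgery". It then splits infection into two grades: "Infection will be defined as major and minor, with major indicated by return to the operating room for irrigation and debridement", and "Minor infection is represented by documentation of cellulitis or superficial infection at surgical site and administration of oral antibiotics". The next bullet describes the superficial form again: "Superficial infection as indicated by documentation of cellulitis at surgical site and administration of oral antibiotics with the indication of wound problems". Nothing else in the protocol defines infection. No culture, clinical sign, diagnosis or adjudication is required.

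Other sections foresee returns to the OR without tying them to infection. Biomedical Research item 1 states: "If patient returns to the OR for repeat debridement procedures, the injection will be repeated". It adds that the second injection "will be given two days later than the first injection". The Recruitment appendix, item 7, says that some wounds cannot be closed at the first operation and need a further one.

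Sample size item 3 rests on this outcome: "we assumed that the no treatment group would have a 10% infection rate, and the treatment group would have a 1% infection rate", with one-sided alpha 0.05, 70% power and 60 per group. Data from several sites are to be combined. What the other sites supply is described as follows: "We will receive de-identified subject demographics, infection information, pertinent dates, surgical procedures performed, and information re: treatment".

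**The concern.** There are two separate gaps.

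**Events that may not be infections.** The marker for major infection is a procedure, and the plan attaches no reason to it. The second minor wording does attach one (wound problems). Debridement can be repeated in an open fracture without infection, and the protocol provides for that inside the 6-week window. Two assessors working from the same text could classify the same patient differently on the sole primary endpoint.

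**Infections that are not events.** Both minor wordings make oral antibiotics a condition. A patient with documented cellulitis at the surgical site who receives only IV antibiotics and does not go back to the OR meets neither grade.

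Counted non-infectious returns dilute the treatment effect, and missed infections remove events. Few events are expected: 10% of 60 is 6 in the control arm and 1% of 60 is 0.6 in the treated arm. A handful of reclassified patients could therefore change the result.

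**Working it through.** **1. The texts side by side**

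| Patient (within 6 weeks) | Literal reading | Grading reading |
|---|---|---|
| Repeat debridement at two days, no infection documented | Event (major) | Not an event |
| Return to the OR for irrigation and debridement because of infection | Event (major) | Event (major) |
| Documented cellulitis, oral antibiotics | Event (minor) | Event (minor) |
| Documented cellulitis, IV antibiotics only, no OR return | Neither category | Infection, but neither grade applies |

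The first row depends on the reading, and no passage chooses between the two. The last row has no category under either.

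**2. The plan's own figure**

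Inputs from sample size item 3: p1 = 0.10, p2 = 0.01, one-sided alpha 0.05, power 70%. The pooled-variance normal formula is

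n = [z(0.95)·√(2p̄(1−p̄)) + z(0.70)·√(p1(1−p1) + p2(1−p2))]² / (p1−p2)²

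With p̄ = 0.055:

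n = [1.645 × 0.3224 + 0.524 × 0.3161]² / 0.09² = 59.8, so 60 per group.

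The plan's figure is reproduced. Power at n = 60 is

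Φ{[(p1−p2)√n − 1.645·√(2p̄(1−p̄))] / √(p1(1−p1) + p2(1−p2))} = Φ(0.528) = 0.701.

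**3. Illustration of misclassification**

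The documents give neither rate, so q and m below are assumed. They are taken as equal in both arms, and 10% and 1% are taken as true infection rates.

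- q = share of patients with a counted non-infectious return, independent of infection: p\* = 1 − (1−p)(1−q).
- m = share of infections missed because treatment was IV only: p\* = p(1−m).

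Example, q = 0.01: 1 − 0.90 × 0.99 = 0.109 and 1 − 0.99 × 0.99 = 0.0199. The power formula gives Φ(0.348) = 0.636.

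| Assumption | Rates | Formula power | Exact power |
|---|---|---|---|
| None | 10.0% vs 1.0% | 70% | 80% |
| q = 1% | 10.9% vs 2.0% | 64% | 71% |
| q = 2% | 11.8% vs 3.0% | 58% | 63% |
| q = 5% | 14.5% vs 6.0% | 46% | 47% |
| m = 10% | 9.0% vs 0.9% | 66% | 76% |
| m = 20% | 8.0% vs 0.8% | 61% | 71% |
| q = 1% and m = 10% | 9.9% vs 1.9% | 59% | 66% |

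Exact power enumerates the uncorrected pooled z-test. The plan says only that a one-sided test for proportions will be used, and the exact column depends on that choice: with Fisher's exact test the baseline is 56%, not 80%.

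**4. Type I error**

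With true infection at 10% in both arms, the exact one-sided type I error of the same z-test stays between 0.050 and 0.054 across the single-assumption rows (each q and each m).

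**5. If 10% and 1% already describe the endpoint as written**

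Then q cannot exceed 1%, because the treated arm has only 1% in total. True infection is 1 − (1−p)/(1−q). At q = 1% this is 9.1% vs 0%, and limiting events to infection would raise formula power from 70% to 78%.

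**The case against.** The strongest reply is that infection is the subject throughout. The outcome is evidence of infection, the sentence opens by defining infection, and the endpoint is later described as its presence. On that view, major and minor only grade an infection already found, and counting an uninfected staged debridement strains the text. This is a fair reading and may be the intended one. It does not close the gap, because no rule says how infection is established before it is graded.

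Several limits on the concern stand:

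- A reader might infer that any return to the OR counts. It does not: the text limits the marker to irrigation and debridement.
- A reader might infer false-positive results or bias between arms. Nothing here shows that. Subject and surgeon are blinded, and equal misclassification leaves type I error near 5%.
- A reader might infer that real power is below 70%. With no rates in the documents, that cannot be claimed. In the z-test enumeration, exact power stays at or above 70% for q up to about 1%, or for m up to 20%, taken singly.
- The IV gap is narrow. It needs documented cellulitis, no qualifying return, and no oral antibiotic for it at any time in the window.
- The list of data from other sites does not mention the indication for a return, but silence does not show that it is omitted. The case report forms are not in the documents, so the indication may already be captured.

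**Conclusion.** The concern holds as a defect of definition. The text supports two event counts for a patient with a non-infectious repeat or staged debridement, and it leaves IV-only cellulitis without an OR return uncounted. This goes beyond missing detail, because applying the stated rules as written can give a wrong count on the sole primary endpoint. It should be fixed before outcomes are assessed.

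The size is not known. The power figures rest on assumed rates, equal misclassification in both arms, 60 per arm, and 10% and 1% taken as true infection rates. They show only that small rates can matter in a trial planned at 70% power.

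The start of the window is a housekeeping matter. The hypothesis counts 6 weeks from administration, and item 2 counts from surgery. These coincide when the wound is closed and injected at the first operation. They differ by about two days for a repeat injection, and by an unstated amount when closure is delayed. A reader might take this for a second material flaw, but the documents do not support that.

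**What to change.** In Statistical Considerations item 2:

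- **Major infection:** an OR return for irrigation and debridement with suspected or confirmed infection documented as the indication, or with infection documented as an operative finding. A planned, staged or repeat debridement without either is not an event.
- **Other infection:** any other documented surgical-site infection (cellulitis, superficial, or deep without an OR return) counts when antibiotics are given to treat it, by any route. Continued open-fracture prophylaxis does not count.
- **Data:** record the indication for each OR return on the UVA case report form, if it is not already there, and request the same item from the other sites. UVA does not oversee those sites and cannot bind their definitions, but with this item one definition can be applied to the pooled data.

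As housekeeping, use the same window start in the hypothesis and in item 2.

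These changes define what is counted and leave care unchanged. The cost is two changes of wording, one form field and one requested item, with no extra patients, visits or procedures. One small downside is that the indication is judged from the notes, so an infection that was not documented is missed.

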**3. Provide a justification for the sample size used in this protocol.**

A sample size analysis was completed for different alpha and power levels. A one-sided test for proportions was chosen to compare the baseline (no treatment) group to the hypothesized proportion (treatment group); based on historical data, we assumed that the no treatment group would have a 10% infection rate, and the treatment group would have a 1% infection rate. Using an alpha of 0.05 and power of 70%, we would need to have 60 patients in each group.

With an expected accrual rate of 65 patients per year, we would expect to enroll 130 patients in two years. In order to maintain the sample size needed to ensure statistically valid results, we would want to enroll approximately 133 patients over the study period to end up with at least 120 patients in the analysis.

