## Brief Summary/Abstract

The primary objective of this study is to investigate the effectiveness of local antibiotic versus placebo in the prevention of infections in open fractures. The study will assess whether local treatment of open fractures with the antibiotic tobramycin (in addition to standard systemic antibiotics) will decrease the risk and rate of infection, time to fracture union, and rate of re-operation. This will be studied using a randomized controlled clinical trial design in adult population of age 18-70 years who present with open fractures. About 133 subjects will be recruited in this study at UVA. There will also be similar studies performed at University of Florida- Jacksonville and Medical University of South Carolina and we will be performing a collaborative site analysis study with those centers and we will be sharing demographic, infection and treatment information (at either 2 or 6 weeks), and any adverse events that occur.

**Note:** Standard protocols at UVA will be followed for systemic antibiotic administration. No specimens will be collected for research purposes. The patient will otherwise receive the standard of care treatment for their fractures.

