#### **Subjects- see below**

- 1. Provide target # of subjects (at all sites) needed to complete protocol.** 133
- 2. Describe expected rate of screen failure/ dropouts/withdrawals from all sites.**

Approximately, 20% of subjects will be lost to follow up

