**3. How many subjects will be enrolled at all sites? 133**

**4. How many subjects will sign a consent form under this UVa protocol? 133**

**5. Provide an estimated time line for the study. 2 years**

### **Inclusion/Exclusion Criteria**

**1. List the criteria for inclusion**

- Ages 18 – 70 years
- Gustilo Type I,II,IIa open fracture (s)
- Ability to provide informed consent (or proxy consent in cases where subject is temporarily impaired when intubated and sedated)
- Subject should be able to follow up at the scheduled times following surgery
- Subjects who may have compartment syndrome, renal insufficiency, and those who are immunosuppressed regardless of antibiotic administration will also be included in the study
- 

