**6. Have you been working with a statistician in designing this protocol? Yes**

IF YES, what is their name? [name]

Will data from multiple sites be combined during analysis? Yes

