**2. List the procedures, in bullet form, that will be done for RESEARCH PURPOSES as stipulated in this protocol.**

- Medical record review at baseline and all subsequent study weeks up to 1 year after surgery
- Randomization to Antibiotic ( tobramycin) arm or Placebo before surgery by clinical pharmacy program at UVA.
- Experimental group will have the close wound injected with 80 mg/40mL of tobramycin at the END of surgery
- Control group will have 40 mL 0.9%NS injected into the closed wound at the end of the case
- Follow up at 2 and 6 weeks at the clinic. *These visits to the clinic will coincide with the follow up as in standard of care for open fracture management.*

**3. Will you be using data/specimens in this study that were collected previously, with the use of a research consent form, from another research study? NO**

**4. Will any of the procedures listed in item # 2 have the potential to identify an incidental finding? This includes ALL procedures, assessments and evaluations that are being done for RESEARCH PURPOSES that may or may not be considered investigational. yes**

► IF YES, check one of the following two options:

The examination(s) utilize(s) the same techniques, equipment, etc., that would be used if the subject were to have the examination(s) performed for clinical care. **There exists the potential for the discovery of clinically significant incidental findings.**

- The PI takes full responsibility for the identification of incidental findings:
- The PI will inform the subjects verbally of all incidental findings that are of clinical significance or are of questionable significance.
- A follow-up letter describing the finding should be provided to the subject with instructions to either show the letter to their PC or if the subject has no PCP, the subject should be instructed to make an appointment at UVa or at the Free Clinic.

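### Enrolling 133 leaves 120 for analysis only at 9.8% loss, but the protocol expects about 20%, which would leave about 106 and cut planning-formula power from 70% to about 65%

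*Combined protocol and SAP*

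**What the plan says.** Statistical Considerations item 3 assumes infection rates of 10% without and 1% with local antibiotic, a one-sided test, alpha 0.05 and 70% power. It arrives at 60 patients per group, then moves to enrolment: "we would want to enroll approximately 133 patients over the study period to end up with at least 120 patients in the analysis". It gives no loss rate for that step. On accrual it says: "With an expected accrual rate of 65 patients per year, we would expect to enroll 130 patients in two years".

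The only loss rate in the document is in Subjects item 2: "Approximately, 20% of subjects will be lost to follow up". It has no time point. The primary outcome is infection within 6 weeks of surgery.

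The meaning of 133 varies:

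- Abstract: "About 133 subjects will be recruited in this study at UVA", with similar studies at two other centres.
- Subjects item 3: "How many subjects will be enrolled at all sites? 133". Item 1 gives 133 as the target over all sites, and item 4 gives 133 as the number consenting under the UVA protocol.
- Statistical Considerations item 6: "Will data from multiple sites be combined during analysis? Yes".

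**The concern.** Two current statements about the same 133 patients cannot both be right. If about a fifth are lost, 120 are not left. If 120 are left, the loss is about a tenth.

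The analysed number and the 70% power are the plan's whole stated basis for its size, and item 3 itself ties 120 to the validity of the result. Planned power is already low, so there is little margin for a shortfall. As written, a reader cannot tell whether the trial is planned on 10% or 20% loss, or whether 133 counts one site or all of them.

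**Working it through.** **Inputs.** From Statistical Considerations item 3: p1 = 0.10, p2 = 0.01, one-sided alpha 0.05 (z = 1.645), power 70% (z = 0.5244), 60 per group, 133 enrolled, at least 120 analysed. From Subjects item 2: 20% lost. From Statistical Considerations item 2: 60 to 65 open fractures a year at UVA.

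**1. Reproduce the plan's 60 per group.** Pooled normal-approximation formula, mean rate 0.055:

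n = [1.645 × √(2 × 0.055 × 0.945) + 0.5244 × √(0.10 × 0.90 + 0.01 × 0.99)]² / 0.09²

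= [1.645 × 0.3224 + 0.5244 × 0.3161]² / 0.0081 = (0.5303 + 0.1658)² / 0.0081 = 59.8, so 60 per group.

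The plan's figure is reproduced. The unpooled version gives 59. The plan does not say which it used; the pooled form matches exactly and is used below.

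**2. Loss implied by 133 to 120.** 1 − 120/133 = 13/133 = 9.8%. A 10% allowance fits (120/0.90 = 133.3). A 20% allowance does not: 120/0.80 = 150, and even the common slip of multiplying by 1.2 gives 144.

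**3. Number analysed at the stated 20%.** 133 × 0.80 = 106.4, about 53 per group. The shortfall is 120 − 106.4 = 13.6.

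**4. Power by the same formula.** Power = Φ{[0.09 × √n − 0.5303] / 0.3161}.

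- n = 60: (0.6971 − 0.5303)/0.3161 = 0.528, power 70.1%.
- n = 53: (0.6552 − 0.5303)/0.3161 = 0.395, power 65.4%.

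**5. Dependence on the test.** The plan names only a one-sided test for proportions. Exact power by binomial enumeration:

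| Test | 60 per group | 53 per group |
|---|---|---|
| Pooled z, uncorrected (true size up to 6.1% and 6.0%) | 80.2% | 75.4% |
| Boschloo (holds 5%) | 68.6% | 61.5% |
| Fisher | 55.5% | 46.5% |

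The level differs widely, but power falls under every test, by about 5 to 9 points.

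**6. What would close the gap.** About 26.6 patients are lost at 20% (133 × 0.20). Recovering a 6-week outcome for 13.6 of them (51%) restores 120. So would about 17 further patients from other sites, since 17 × 0.80 = 13.6.

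**7. Accrual, if UVA is the only source.** Item 2 counts 60 to 65 "open fractures within a year to be treated at UVA based on historical records". The assumed 65 enrolled a year is the top of that range, with no allowance for refusals or exclusions. Even if every fracture were enrolled, two years give 120 to 130, and 133 takes 133/65 = 2.05 to 133/60 = 2.22 years.

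**The case against.** The strongest reply is that 106 is conditional.

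- **Other sites.** The abstract puts the 133 at UVA and item 6 combines data across sites, so patients from elsewhere could make up the difference, and only about 17 are needed. Parts of the outside-institution sections are also absent from the text available for review. This stands as a limit on the 106. However, Subjects items 1 and 3 give 133 for all sites, and the sample size justification does not draw on any additional patients.
- **What the 20% means.** It has no time point, and the question it answers also covers screen failures and withdrawals. Loss by 6 weeks could be lower, and the planned research procedures include "Medical record review at baseline and all subsequent study weeks up to 1 year after surgery", which could recover outcomes. The missing time point and the record review stand as caveats. The breadth of the question helps little: the answer speaks only of loss to follow-up, and 133 is already the number enrolled and consented.
- **Size.** By formula the drop is about 5 points, and the uncorrected z-test still has 75.4% exact power at 53 per group. But that test exceeds its nominal 5%. Boschloo's test, which holds the level, is below 70% at both sizes.

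None of this reconciles 9.8% with 20%.

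**Conclusion.** The concern holds. The step from 133 enrolled to 120 analysed needs 9.8% loss, while the protocol's only stated loss rate is about 20%. On that rate about 106 would be analysed (53 per group), 14 short of the stated minimum, and power by the planning formula is 65.4% rather than 70.1%.

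The mismatch between the loss rates is certain. The 106 and the 65% rest on two assumptions that the text leaves open: 133 is the total across sites, and patients lost to follow-up contribute no 6-week outcome. The size of the power drop also depends on the test used. The accrual point is secondary and applies only if UVA supplies all patients.

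**What to change.** Keep 133 and restate Statistical Considerations item 3, for example:

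*With 133 patients enrolled and 20% lost to follow-up, about 106 (53 per group) will be analysed. By the pooled normal-approximation formula this gives about 65% power to detect 10% versus 1% at one-sided alpha 0.05.*

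If about 10% loss at 6 weeks is what was meant, correct Subjects item 2 instead, state the time point and give the basis for the lower rate. In that case 133 × 0.90 = 119.7, which matches 120 only because the plan says approximately 133.

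Either way:

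- Make the abstract, Subjects items 1, 3 and 4, and Statistical Considerations item 6 agree on whether 133 is UVA only or all sites.
- State which sites supply the 65 patients a year.
- If power is quoted for a particular test, name the test.

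The cost is wording only, with no extra patients and no change to endpoint or allocation. The price of keeping 133 with 20% loss is a less favourable stated power, about 65% instead of 70%.
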